### **3.3.2 Follow-up for withdrawn subjects**

Patients will be routinely followed-up for additional 7 days after the patch removal. They will be contacted by phone (if discharged) or visited on the floor (if in the hospital). If discharged, they will be provided with the phone number of the PI and research staff in case of occurrence of any problems.

## **4.0 Recruitment Methods**

### **4.1 Identification of subjects**

Patients will be identified by the anesthesia providers during their anesthesia pre-op visit in the Anesthesia Preoperative Evaluation Clinic (APEC) at Hershey Medical Center (The PI serves as current Medical Director of the Clinic).

### **4.2 Recruitment process**

Patient will be asked about the history of previous general anesthesia and, if there is history of severe PONV (defined as need to administer additional antiemetic medication postoperatively) associated with previous anesthetics, in particular delayed (defined as post-PACU) or post-discharge, the patient will be offered opportunity to enroll into the study protocol.

### **4.3 Recruitment materials**

None will be used. The information about previous history of PONV will be obtained during routine history and physical evaluation in the Clinic.

### **4.4 Eligibility/screening of subjects**

A detailed PONV history will be used to determine occurrence/severity of previous PONV during patient's history and physical evaluation in the Clinic (as it is done anyway for all surgical patients seen in APEC). In general the eligible patients experienced 1 or more episode of PONV with general anesthesia requiring additional treatment in PACU or had episodes of PONV after discharge from PACU or discharge from hospital.

## **5.0 Consent Process and Documentation**

### **5.1 Consent Process**

The informed consent for the study will be obtained in APEC

#### **5.1.1 Obtaining Informed Consent**

##### **5.1.1.1 Timing and Location of Consent**

Consent to participate will be obtained from eligible patients after preoperative evaluation in the Anesthesia Preoperative Evaluation Clinic (APEC) during the patient's routine preoperative visit.

##### **5.1.1.2 Coercion or Undue Influence during Consent**

The patient will be advised that participation in research studies is voluntary and that their decision to participate or not participate will not affect the level of care at this institution.

#### **5.1.2 Waiver or alteration of the informed consent requirement**

Not applicable

## **5.2 Consent Documentation**

### **5.2.1 Written Documentation of Consent**

We will obtain a consent form signed by the patient and the person obtaining the consent. An original signed copy will be retained by the patient and the research team and a copy will be placed in the patient's medical record.

### **5.2.2 Waiver of Documentation of Consent**

Not applicable

## **5.3 Consent – Other Considerations**

Not applicable

## **6.0 HIPAA Research Authorization and/or Waiver or Alteration of Authorization**

Authorization will be obtained and documented as part of the consent process.

## **7.0 Study Design and Procedures**

### **7.1 Study Design**

This will be an open label, prospective pilot study.

### **7.2 Study Procedures**

Patients will be recruited from the surgical population undergoing preoperative evaluation in Anesthesiology Preoperative Evaluation Clinic at Hershey Med. Ctr. (~15,000 per year). Selected patients (ASA 1-3, N=60) with history of severe PONV after one or more of previous general anesthesia, and scheduled to undergo surgical procedures with general anesthesia will be enrolled into IRB approved protocol. The patch will be placed by the patient at home 24 – 48 hours before surgery as directed by the doctor. The subsequent standardized general anesthesia protocol for elective surgery will include general endotracheal anesthesia with sevofluran, including standard intraoperative PONV prophylaxis (IV dexamethasone and 4 mg and diphenhydramine 25 mg ). Postoperative evaluation will include recording of incidence and severity of PONV at the time of discharge from PACU (acute PONV), and at 120 hrs (delayed or post discharge PONV). The final phone interview will be performed 7 days after patch removal in order to capture possible side effects after discontinuation of medication.

#### **7.2.1 Visit 1 - Anesthesia Preoperative Evaluation Clinic and recruitment and drug dispensation**

Patient is seen in clinic and identified as having a history of serious PONV, in particular delayed or post discharge PONV. Study will be explained to the patient and consent obtained. The investigational pharmacy will be notified that a study patient has been enrolled and they will prepare the patches for distribution to the patient. EKG will be performed and the results will be recorded preoperatively.

A member of the research team will obtain the assigned patches from the investigational pharmacy and deliver to the anesthesia provider (member of the research team).

The provider will then demonstrate to the patient how to apply the patch and the patient can practice using a placebo patch to show that the correct placement. Patient will then take the actual patch home with them. Patient will also be given a PONV diary to take home with them. Upon returning home from surgery, the patient will be asked to record their instances of nausea and vomiting on a daily basis for up to five days after surgery. At hour 120 post-op, a case manager will telephone the patient and note any recorded

instances of nausea and vomiting since the patient has returned home. The case manager will also check the status of the patch and any medications that were taken as a result of nausea and vomiting. One week after removal of patch (120h post-op + 7 days), a case manager will call the patient a final time to collect adverse events and to assess patient satisfaction with the patch.

#### **7.2.2 Visit 2 - approximately 24-48 hours preoperatively (patient's home)**

Patient will apply the patch to their upper arm 24-48 hours before scheduled surgical procedure, as instructed during their pre-op anesthesia visit. The patch will then remain in place until 120 hours after surgical procedure. No backup patch will be provided so the patients with the accidentally missing patch will need to call their primary surgical service for the standard antiemetic medication.

#### **7.2.3 Visit 3- Day of Surgery**

Patient will arrive for surgery. A member of the research team will meet them in the SDU and record the time that the patch was applied, and if it has been placed correctly, intact and still in place. Any potential side effects (systemic or local) will be recorded at that time. The subsequent standardized general anesthesia protocol for elective surgery will include general endotracheal anesthesia with sevofluran (no nitrous oxide), muscle relaxants (with reversal), intraoperative IV opioid analgesics, including standard PONV prophylaxis (dexamethasone and [diphenhydramine 25 mg IV](#) ).

Early postoperative evaluation will include recording of incidence and severity of PONV at the time of discharge from PACU (acute PONV). The incidence of vomiting or retching will be recorded by the nursing staff. Patients with symptoms requiring a rescue antiemetic—nausea score  $\geq 4$  on an 11-point Numeric Rating Scale (NRS), retching or vomiting, or patient request—within 6 hours of PACU admission will be given the first line rescue medication promethazine IV 6.25mg as per current standard of care. Promethazine will be used as slow infusion bolus (over 5-10 min) in large, good flowing peripheral IV. If the first line rescue medication does not work the patient will be given ondansetron 4 mg IV). The NRS is an 11-point linear scale on which patients rate their nausea, with 0 meaning no nausea and 10 meaning the worst possible nausea.

The subsequent evaluations will be performed either at the patient's bed (if in the hospital) or by phone call at 120 hrs (delayed or post discharge PONV). The patient will be supplied with a diary to record the information that will be requested on the follow-up phone calls.

The primary efficacy endpoint will be complete response (CR), defined as no emetic episode and no rescue medication; the proportions of patients with no emesis and no additional rescue medication in the 120 hours following the completion of surgical procedure and the change from baseline nausea score using the NRS. Treatment-emergent adverse events (TEAEs), regardless of suspected causal relationship to the study medication, will be also recorded throughout and continued until 5 days after surgery.

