### **1.2 Primary Study Endpoints**

Number of complete responders (CR, defined as no nausea or vomiting/retching episodes during 120 hours postoperatively, no additional antiemetic medication up to 120 hours after surgery)

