## **2.0 Background**

### **2.1 Scientific Background and Gaps**

Postoperative nausea and vomiting (PONV) are common and distressing symptoms to patients. The general incidence of vomiting is about 30%, the incidence of nausea is about 50%, and in a subset of high-risk patients, the PONV rate can be as high as 85%. Unresolved PONV may result in prolonged post anesthesia care unit (PACU) stay and unanticipated hospital admission that result in a significant increase in overall health care costs. The goal of PONV prophylaxis is therefore to decrease the incidence of PONV and thus patient-related distress and reduce health care costs. The major shortcoming of currently used antiemetics is their relatively short duration of prophylactic activity (e.g., about 4-6 hours for all 5HT3 receptor antagonists- 5HT3RA)

requiring its repeated dosing or, for longer acting antiemetics (e.g., scopolamine patch or dexamethasone), the presence of significant side effects and limited effectiveness.

It was reported previously that IV granisetron could be more effective than other 5HT3RA antiemetics because of its unique metabolic pathways and stronger 5HT3 receptor affinity. It is therefore important to investigate if the administration of granisetron in the prolonged activity formulation will provide effective antiemetic prophylaxis beyond 24-48 hours after administration.

It is proposed that the non-invasive patch application could extend the available repertoire of the current 5HT3RAs oral or IV regimens in PONV. Sancuso® was approved by the United States (US) Food and Drug Administration (FDA) in September 2008, and is indicated for the prevention of nausea and vomiting in patients receiving moderately and/or highly emetogenic (HE) chemotherapy regimens of up to 5 consecutive days' duration. The present study will evaluate its effectiveness in the prophylaxis of PONV.

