### **9.0 Statistical Plan**

#### **9.1 Sample size determination**

We are planning an open label study of cases treated with granisetron patch (no comparison group, historical control group). Prior data indicate that the failure rate (at least 1 x PONV postoperatively or administration of additional antiemetics) among patients with severe PONV is 0.85. If the true failure rate for experimental subjects is 0.4 (decrease of incidence of PONV by half), we will need to study 60 experimental subjects to be able to reject the null hypothesis that the failure rates for experimental subjects is equal to historical control with probability (power) 0.8. The Type I error probability associated with this test of this null hypothesis is 0.05. We will use an uncorrected chi-squared statistic to evaluate this null hypothesis.

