#### **9.2 Statistical methods**

The Type I error probability associated with this test of this null hypothesis is 0.05. We will use an uncorrected chi-squared statistic to evaluate this null hypothesis.

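### The primary complete response counts nausea alone as failure in 1.2 but not in 7.2.3, and Section 9 does not say which version is tested against 0.85

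*Combined protocol and SAP*

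**What the plan says.** The combined protocol and SAP defines the primary endpoint in two places.

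- **Section 1.2** counts complete responders, who must have "no nausea or vomiting/retching episodes during 120 hours postoperatively" and no additional antiemetic over the same period.
- **Section 7.2.3** says: "The primary efficacy endpoint will be complete response (CR), defined as no emetic episode and no rescue medication". The same sentence then lists "the change from baseline nausea score using the NRS" as a further element. No analysis of that score is given anywhere.

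Section 9.1 describes the comparison as "no comparison group, historical control group". It sets the historical "failure rate (at least 1 x PONV postoperatively or administration of additional antiemetics") at 0.85 and the hoped-for rate on the patch at 0.40, with 60 patients. Section 9.2 adds only the error rate and the test: "We will use an uncorrected chi-squared statistic to evaluate this null hypothesis". It does not name the endpoint.

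The only other mention of this rate is in Section 2.1: "in a subset of high-risk patients, the PONV rate can be as high as 85" per cent. Neither section gives a source or a time window for it.

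**The concern.** Both definitions are current text and both are labelled primary. They disagree on one group: patients who feel sick but neither vomit or retch nor take an antiemetic. An analyst could follow either section and remain within the protocol.

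This matters more here than in a randomised trial. The study is open-label with a single arm, so the inference rests on the endpoint definition and one historical rate. If that rate counts nausea and the endpoint does not, the comparison is not like with like. The headline result, the proportion of complete responders, also depends on which section is used, whatever the test shows.

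**Working it through.** **Plan's own figure.** A one-sample calculation for 0.85 against 0.40 (two-sided 0.05, power 0.8) gives n = [(1.96·√(0.85·0.15) + 0.842·√(0.40·0.60)) / 0.45]² = 6.1, so 7 patients. A two-group calculation gives 17 per group. The stated 60 is not reproduced. That is a separate matter; 60 is used below as stated.

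**Step 1: compare the definitions.**

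| Patient's course to 120 h | 1.2 | 7.2.3 | 9.1 |
|---|---|---|---|
| Any vomiting or retching | failure | failure | failure |
| Any antiemetic given | failure | failure | failure |
| Nausea only, no antiemetic | failure | response | probably failure, not stated |
| None of these | response | response | response |

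This takes rescue and additional antiemetic as the same thing, and an emetic episode as vomiting or retching. Every 7.2.3 failure is then a 1.2 failure. If q is the share of all patients in the third row, the 7.2.3 failure rate equals the 1.2 failure rate minus q.

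**Step 2: how large the third row can be.** Section 7.2.3 provides rescue for a nausea score of 4 or more, retching or vomiting, or patient request, within 6 hours of PACU admission. That leaves early nausea below 4 without a request, and later untreated nausea up to 120 hours. The documents do not give q. The only anchor is from general surgical patients in Section 2.1: "general incidence of vomiting is about 30%, the incidence of nausea is about 50" per cent. So at least 0.50 − 0.30 = 0.20 have nausea without vomiting, but how many of them go untreated is unknown. The values of q below are therefore scenarios.

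**Step 3: the cut-off.** Assumed, because not stated: a one-sample, two-sided test against a fixed 0.85. Expected failures are 60 × 0.85 = 51, with SD √(60 × 0.85 × 0.15) = 2.766.

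- 45 failures: z = (45 − 51)/2.766 = −2.169, χ² = 4.706, p = 0.030.
- 46 failures: z = −1.808, χ² = 3.268, p = 0.071.

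The test favours the patch at 45 or fewer failures.

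**Step 4: no patch effect.** Let the nausea-inclusive failure rate stay at 0.85. The chance of declaring benefit is P(X ≤ 45), with X binomial(60, 0.85 − q).

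| q (points) | 7.2.3 failure rate | Chance of declaring benefit |
|---|---|---|
| 0 (definitions agree) | 0.85 | 2.9% |
| 1 | 0.84 | 4.8% |
| 2 | 0.83 | 7.5% |
| 5 | 0.80 | 21% |
| 10 | 0.75 | 55% |

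For example, 51 failures under 1.2 (9/60 = 15% responders) become 45 under 7.2.3 (15/60 = 25%, p = 0.030) if six patients had untreated nausea only.

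**Step 5: other forms of the test.** Against a finite historical sample held at exactly 85%, the chances are lower. With 200 historical patients (cut-off 44) they are 13% and 43% at 5 and 10 points; with 60 (cut-off 42) they are 4% and 22%. These sample sizes are illustrations, not from the documents. Holding the historical count fixed makes these conditional figures. A one-sided one-sample test (cut-off 46) gives 5.8%, 31% and 67% at 0, 5 and 10 points.

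**Step 6: an effective patch.** At a failure rate of 0.40, P(X ≤ 45) is 1.000 to three decimals under either definition. At a nausea-inclusive 0.60, the 1.2 version already rejects in 99.5% of one-sample trials.

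**The case against.** The strongest reply is that the protocol already points to 1.2. That section carries the heading for primary endpoints, and the failure definition in 9.1 is worded in terms of PONV, a term whose own name includes nausea. Harm to the test needs an analyst to depart from that reading. This lowers the likelihood but does not remove the conflict, because 7.2.3 expressly calls its own version primary and 9.1 never says that nausea alone is a failure.

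Second, the rescue rule makes much early nausea a failure under both definitions. That stands and limits the size. It does not cover most of the 120 hours, and delayed and post-discharge symptoms are the study's particular interest.

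Third, this is labelled a pilot, and at the planned effect the test rejects either way. That also stands for the test, though not for the reported response rate.

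A reader might infer that testing the 7.2.3 version against 0.85 must favour the patch. The documents do not support that. It needs 0.85 to be a nausea-inclusive rate over 120 hours, and no source or window is given. If 0.85 describes a shorter period, counting failures over 120 hours works against the patch, and the net direction could reverse. Nor do the documents support reading any row of the scenario table as this trial's error rate.

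**Conclusion.** The contradiction is real and needs correcting before analysis. Two current sections define the primary complete response differently, and the statistical section does not choose between them.

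What follows from the definitions, on the wording assumption in Step 1, is that the 7.2.3 response rate is equal to or higher than the 1.2 rate in the same patients. The effect on the test is conditional: if 0.85 is a nausea-inclusive 120-hour rate, the mismatch is neutral or favours the patch. Its size then depends on a share that the documents do not give, from no change at 0 points to a 21% chance of a false claim at 5 points and 55% at 10, in the one-sample two-sided version. The test is at risk mainly when the patch has little effect. The reported response rate is affected at any effect size if such patients exist.

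**What to change.** 1. In 7.2.3, replace the primary endpoint sentence with: 'The primary efficacy endpoint is complete response as defined in Section 1.2, that is, freedom from nausea, from vomiting or retching, and from additional antiemetic medication for 120 hours after surgery.'
2. In 9.1 and 9.2, add: 'Failure is any departure from complete response as defined in Section 1.2, including nausea alone. This is the endpoint tested.'
3. Make the emesis-and-rescue-free proportion and the NRS nausea score secondary endpoints, not tested against 0.85.
4. In 9.1, give the source of 0.85 and confirm that it uses the same definition and time window. If it does not, state the mismatch as a limit on the conclusion.

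The cost is wording in three sections and documentation of one rate. No change in sample size is needed for this point. The downside for the sponsor is that the reported complete response rate will be equal to or lower than under 7.2.3. How nausea is recorded for patients still in hospital is a separate data-capture question and is not part of this point.

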### **1.3 Secondary Study Endpoints**

Frequency and severity of nausea and vomiting during the observed period, patient satisfaction scores, length of stay, frequency of re-admission, frequency and type of side effects

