## 2.3 Study Rationale

Clinical guidelines recommend the use of 5HT3RAs in the prevention of PONV and chemotherapy-induced nausea and vomiting (CINV). Granisetron is a potent 5HT3RA, with little or no affinity for other serotonin receptors, or for dopamine-D2, histamine-H1, benzodiazepine and opioid receptors.

Oral and intravenous (iv) formulations of granisetron have been marketed for over 15 years. They are licensed for the prevention of PONV and nausea and vomiting associated with initial and repeat courses of emetogenic cancer therapy, including high-dose cisplatin, which has a strong emetic effect in more than 90% of patients.

ProStrakan, Limited has developed a new granisetron formulation, Sancuso® , a transdermal delivery system (TDS) (granisetron TDS or patch) for the prevention of CINV. Sancuso® consists of a stable matrix of granisetron base (6% w/w) in a commercially-available adhesive (DURO-TAK ® 387-2287), designed to sustain delivery of granisetron over a number of days following topical application. Pharmacokinetic evaluation of Sancuso ® has indicated that it provides continuous delivery of granisetron over 7 days, providing exposure similar to an oral dose of 2 mg per day (Howell et al, 2009). Previous data indicate prolonged activity of this preparation in prophylaxis of CINV. There is no data available about the efficacy of this formulation in the prophylaxis of PONV.

It should be noted however that there is increasing concern among anesthesiologists and surgeons about patients displaying so called post-discharge (or late) form of PONV. These symptoms occur at least 48-72 hours after the procedure and may last several days (often after patient has been already discharged from the medical facility). It is therefore feasible that the investigated formulation of granisetron will provide prophylactic antiemetic activity throughout the entire period, including acute and delayed phases of PONV.

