### 3.2 Exclusion Criteria

- Allergy to granisetron or other 5HT3RA drugs
- Previous allergic reactions to any drug skin patches
- Recent (less than 1 month) or current chemo- or radiotherapy
- Any nausea, vomiting, or retching within 24 hours prior to anesthesia
- Any type of eye surgeries
- History or diagnosis of gastrointestinal obstruction or ileus
- History of serotonin syndrome
- Unable to sign consent

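### The change-from-baseline nausea score has no recorded baseline, and the severity schedule does not assure a rating of late nausea (from 48-72 h)

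*Combined protocol and SAP*

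**What the plan says.** **The measure.** Section 7.2.3 ends its primary efficacy endpoint sentence with "the change from baseline nausea score using the NRS". The NRS is an 11-point scale, "with 0 meaning no nausea and 10 meaning the worst possible nausea". Section 1.3 instead lists among the secondary endpoints "Frequency and severity of nausea and vomiting during the observed period", without naming a scale or a summary.

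**The baseline.** Section 3.2 excludes patients with "Any nausea, vomiting, or retching within 24 hours prior to anesthesia". On the day of surgery staff "record the time that the patch was applied, and if it has been placed correctly, intact and still in place", and note any side effects. Neither this check nor the clinic visit in 7.2.1 includes an NRS rating.

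**The schedule.** Section 7.2 provides for "recording of incidence and severity of PONV at the time of discharge from PACU (acute PONV), and at 120 hrs". Sections 7.2.3 and 11.4 add no timed assessment between these two points.

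**The diary and the call.** Under 7.2.1, once home, "the patient will be asked to record their instances of nausea and vomiting on a daily basis for up to five days after surgery". The same section lists what the 120 h call collects: recorded instances since the return home, patch status, and medication taken for nausea or vomiting. Section 7.2.3 describes the diary more openly, as holding whatever the follow-up calls will ask about.

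**The target phase.** Of late PONV, section 2.3 says: "These symptoms occur at least 48-72 hours after the procedure and may last several days".

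**The concern.** A change score needs a baseline that is measured and can vary between patients. Here none is scheduled, and the most natural time to take one, shortly before anesthesia, is where eligibility forces it to 0.

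The second problem is independent of the first. The trial is aimed at patients with delayed or post-discharge PONV, yet the two scheduled severity ratings fall before that phase and at the very end of the observation period. What happens in between depends on a diary whose content is described in two ways, and on a 120 h rating whose recall period is not stated.

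At stake is the severity result promised in 1.3. If staff record current nausea at 120 h, severe nausea on day 3 that has since settled leaves no trace in the severity data. Daily scores that were never recorded cannot be recovered afterwards.

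**Working it through.** The plan gives no figure to reproduce on this point; section 9 contains no analysis of the NRS. The check sets the sections side by side and adds timing arithmetic.

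**1. What the change score equals.** Change at time t = NRS(t) - NRS(baseline).
- Baseline within 24 h of anesthesia: section 3.2 allows no nausea and the scale sets no nausea at 0, so change = NRS(t) - 0 = NRS(t). The subtraction adds nothing.
- Baseline earlier, for example at the clinic visit (at least 24 h before surgery under 3.1): the exclusion does not force it to 0, but no such rating is planned, so the change cannot be calculated.

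**2. The interval between scheduled ratings.** The time of PACU discharge is not given; assume 1-6 h.
- At 1 h: 120 - 1 = 119 h, and 119/120 = 99%.
- At 6 h: 120 - 6 = 114 h, and 114/120 = 95%.

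So 95-99% of the period has no scheduled severity rating inside it. All of the 48-72 h onset window falls in this interval.

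**3. What a current rating at 120 h would detect.** An episode starting at time T is still present at 120 h only if it lasts at least 120 - T.
- T = 48 h: at least 72 h.
- T = 72 h: at least 48 h.

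A shorter episode scores 0 at 120 h whatever its peak.

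**4. How many episodes that could be.** The documents give no distribution of onset or duration. As an illustration, let T be uniform on 48-72 h, so that the remaining time R = 120 - T is uniform on 48-72 h with mean 60 h. Let duration be independent and uniform on a to b hours. When a is at most 48 and b at least 72, the share over before 120 h is (60 - a)/(b - a).

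| Assumed duration (h) | Calculation | Over before 120 h |
|---|---|---|
| 12-48 | longest duration, 48, does not exceed the shortest R, 48 | 100% |
| 24-72 | 36/48 | 75% |
| 24-96 | 36/72 | 50% |
| 48-96 | 12/48 | 25% |

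Section 2.3 sets the onset as a minimum. Onsets later than 72 h leave less time to resolve and would lower these shares.

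**5. What the other records could supply.** The diary wording in 7.2.1 and its list of items for the 120 h call mention no score. The wording in 7.2.3 leaves room for one, because 7.2 expects severity at 120 h. For patients still in hospital, 7.2.1 specifies no daily record, since that diary starts on the return home.

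**The case against.** The strongest reply is that these are gaps in specification and do not show that the measurement fails. The 120 h contact is labelled as covering delayed or post-discharge PONV, which names a phase, and the call looks back over events since the return home. If the severity rating is a worst-since-discharge recall, or the diary form (not among the documents) holds scores, the loss in steps 3 and 4 does not arise in the same way. This stands, and it limits the conclusion to severity not being assured.

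Three stronger readings are tempting and are not supported.
- *Eligibility fixes the baseline at zero.* It does so only for a baseline within 24 h of anesthesia. The time point itself is undefined.
- *A zero baseline hides late nausea.* It makes the change score redundant and loses no information. Any blind spot comes from the schedule.
- *The trial would miss late nausea, and a near-zero mean change would pass for efficacy.* Complete response in 1.2 requires freedom from nausea for 120 h, and the failure definition in 9.1 counts a single PONV event. Nausea on day 3 is therefore a failure on that endpoint, and section 9 plans no test of the change score. The complete-response wording in 7.2.3 does leave nausea out; that is a separate discrepancy with 1.2.

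The reply does not dispose of the rest. No baseline NRS is scheduled, no severity summary is stated, and no severity rating is explicitly planned between PACU discharge and 120 h.

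**Conclusion.** The point holds in two limited parts.

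First, the change-from-baseline score is either not calculable or identical to the raw score, and 7.2.3 lists it with the primary endpoint although 1.3 treats severity as secondary. This follows from the text without further assumptions.

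Second, late-phase severity is not assured. Ratings are scheduled only at the two ends of an interval that makes up 95-99% of the 120 h, given PACU discharge at 1-6 h. How much would be lost depends on the recall period at 120 h, the diary content and episode durations, none of which is stated. The 25-100% range in the illustration rests on assumed durations and a current rating, and is not an estimate for this trial.

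Occurrence of late nausea remains captured through section 1.2. The change should be made before enrolment: the remedy is cheap and measures severity better than the score now named.

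**What to change.** - Delete the change-from-baseline score from 7.2.3 and keep nausea severity as the secondary endpoint in 1.3.
- Have the patient record the worst NRS (0-10) for each postoperative day in the existing diary, starting at surgery and including days in hospital. Align the diary descriptions in 7.2.1 and 7.2.3 with this.
- State the summaries in section 9: worst score over 0-120 h, and worst score by day. The proportion at NRS 4 or above may be added as a descriptive cut-off. In the protocol that value serves only as a rescue trigger within 6 h of PACU admission, so it should not be presented as an established threshold for late nausea.

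The cost is one extra diary line per day, handing out or using the diary on the ward, and a wording change. The downside is slightly more burden for patients and some missing daily entries. Because a missed day can lower the recorded worst score, the number of completed days should be reported beside it.
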